6.8. Concomitant Therapy

Prestudy therapies administered up to 14 days before first dose of study intervention must be recorded at screening.

Concomitant therapies must be recorded in the CRF throughout the study from the screening visit until the last study-related activity, or until the participant has been deemed lost to follow-up after demonstration of due diligence of follow-up efforts.

In case any comedications are used, the dose and dosing regimen must be recorded in the Concomitant Therapy Section of the CRF. For any concomitant therapy given as a treatment for a new condition or a worsening of an existing condition (relative to the moment of signed ICF), the condition must be documented in the Adverse Event Section of the CRF.

The following medications other than the study intervention are allowed during (a part of) the study:

- The investigator may permit the use of paracetamol/acetaminophen from 3 days before first dose of study intervention until the last PK sample has been taken at ≤3 x 500 mg per day, and ≤3 grams per week. In case paracetamol/acetaminophen is used, the date and time of dosing, the indication, the dose, and the dosing regimen must be recorded in the Concomitant Therapy Section of the CRF. In order to minimize the antipyretic effects of paracetamol/acetaminophen on body temperature outcome readings, participants are recommended not to take paracetamol/acetaminophen within 4 hours before the next body temperature measurement, except those with high fever (≥39°C). In this case, the body temperature before taking paracetamol/acetaminophen, the dose taken, and the body temperature one hour after taking paracetamol/acetaminophen should be recorded in the daily dairy. In addition, the Medical Monitor should be informed about this occurrence.
- Stable HRT (ie, same dose and not starting or stopping HRT for 2 weeks before first dose of study intervention until the end of the study) in postmenopausal women is allowed. It should be noted that JNJ-64281802 may affect the effectiveness of HRT agents when coadministered. The use of HRT must be recorded in the Concomitant Therapy Section of the CRF. Applicable procedures and treatment guidance based on package inserts should be respected.

Other co-medication allowed include the following:

- H₁ receptor antagonists (with exception of mizolastine), topical corticosteroids, or antipruritic agents in the recommended dose scheme.
- H₂ receptor antagonists.

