7. DISCONTINUATION OF STUDY INTERVENTION AND PARTICIPANT DISCONTINUATION/WITHDRAWAL

7.1. Participant Discontinuation Criteria

A participant's study intervention must be discontinued if:

- The participant withdraws consent to receive study intervention.
- The investigator believes that for safety reasons or tolerability reasons (eg, AE) it is in the best interest of the participant to discontinue study intervention.
- The participant becomes pregnant.
- As baseline (Day 1) laboratory results will not be available at randomization, any participant who reports with 2 or more ≥ Grade 2 laboratory abnormalities for ALT, AST, creatinine, lipase, absolute neutrophil count, platelet count, or hemoglobin at baseline, must be discontinued. Discontinuation of study intervention should only occur after a confirmatory retesting result and if deemed clinically significant by the investigator.

- Noncompliance with study intervention administration occurs, defined as missing a LD, 2 consecutive MDs, or 2 nonconsecutive MDs within a week (judged case-by-case after discussion between the Sponsor and investigator).
- In case of abnormal liver tests as outlined in 10.11 Appendix 11: Liver Safety: Suggested Actions and Follow-up Assessments and Section 7.1.2 Participant Stopping Criteria due to Liver Chemistry.

If a participant discontinues study intervention prematurely for any reason other than withdrawal of consent before the end of the double-blind prophylactic dosing phase, a withdrawal visit should be scheduled as soon as possible after the decision for discontinuation, followed by a follow-up visit, which is preferably scheduled 13 to 17 days after the last dose study intervention intake, if the condition of participant allows (see Section 1.3.2.4, Discontinuation From Study Intervention or Study). Blood sample should be collected at the withdrawal and follow-up visits for immune assessments, viral analysis, viral genome sequencing, and safety assessments (at the follow-up visit, safety assessments should occur at the discretion of the investigator).

Study intervention assigned to the participant who discontinued study intervention may not be assigned to another participant. Additional participants will be entered to ensure the protocol-specified number of participants complete the study.

Please refer to Appendix 4: COVID-19 Appendix for guidance on study conduct during the COVID-19 pandemic.

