10.2. Appendix 2: Rash Management

Dengue symptomatic infection is known to result in skin rashes in most patients. Rashes may potentially also be related to the study intervention, and it may not be possible to differentiate between a rash secondary to DENV infection and one related to the study intervention. In all cases of rash that are not related to DENV infection, the below rash management should be followed.

In case a causal relationship between the rash and the study intervention cannot be excluded, then the following visits and assessments will be performed as indicated. Unscheduled follow-up visits for close follow-up of rash will be performed based on the grade (severity) of the rash. At the investigator's discretion, additional visits and assessments can be performed.

If a causal relationship between the rash and the study intervention cannot be excluded, safety blood samples need to be taken during the (unscheduled) visits as described below. The following parameters need to be tested: aspartate aminotransferase (AST), ALT, creatinine, erythrocyte sedimentation rate, and a complete blood cell count (including hemoglobin, hematocrit, red blood cell [RBC] count, white blood cell [WBC] count, neutrophils, lymphocytes, monocytes, eosinophils, basophils, and platelet count).

The rash event should be captured in the Adverse Event Section of the CRF, and in more detail in the specific rash assessment pages of the CRF.

Participants should be informed that they should contact the investigator and visit the study site immediately (unscheduled visit, Day 0 of the rash) when they notice any rash. The skin reaction should be evaluated at the study site the same day (if possible) or the next day. Participants should be advised to contact the investigator immediately if there is any worsening of the rash, if any systemic signs or symptoms appear, or if mucosal involvement develops.

Grading of rash events will be based on the Division of Acquired Immunodeficiency Syndrome (DAIDS) Table for Grading the Severity of Adult and Pediatric Adverse Events (DAIDS 2017).

Monitoring of the evolution of rash events will be performed as described in Table 5 below.

 Table 5:
 Management of Rash Events by Severity Grade

Status: Approved, Date: 19 July 2023

			•	
	Definition	Study	Activities by Day ^a	Referral to Dermatologist
		Intervention		and Dermatology
		Action		Activities

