rash ^b mad or t Syn (pai doe with requone	iffuse, aculopapular rash, target lesions. ymptomatic pain/pruritus) but pes not interfere ith function and/or quires more than ne dose of edication.	Study intervention intake may be continued at the investigator's discretion	 Day 0: Required on-site unscheduled visit for initial rash evaluation, if participant is outside the study site. Safety laboratory assessments are required. Digital pictures^d of skin lesions should be taken (preferred within 24 hours) after the onset of the rash. Cetirizine, levocetirizine, topical corticosteroids, or antipruritic agents may be prescribed. Day 1 and 7: Safety blood samples and digital pictures^d should be taken. After Day 7: If the rash is unresolved: If there is an increase in AST/ALT of ≥2 times the ULN, participants should be followed weekly (or more frequently, at the investigator's discretion) with repeated local laboratory assessments and digital pictures^d until resolution of the AST/ALT abnormalities. If there is no increase in AST/ALT, additional unscheduled visits (including local laboratory assessments and digital pictures^d) can be performed at the investigator's discretion. If the rash evolves from a Grade 2 to a Grade 3-4 rash, additional unscheduled visits have to be conducted according to the guidelines for Grade 3-4 rash. Upon resolution/stabilization of the rash: Digital pictures^d should be taken and the final rash assessment pages of the CRF should be completed 	Not required

	Definition	Study Intervention Action	Activities by Day ^a	Referral to Dermatologist and Dermatology Activities
Grade 3	Diffuse rash AND vesicles or limited	Must permanently	Day 0 : Required on-site unscheduled visit for initial rash evaluation, if participant is outside the study site.	Required ^c
	number of bullae or	discontinue and		Biopsy required within
	superficial	be withdrawn	Day 0 and 1 :	24 hours after onset of
	ulcerations of	from the study;	 Safety laboratory assessments are required. 	rash.
	mucous membrane	no rechallenge	• Digital pictures ^d of skin lesions should be taken within 24 hours after	
	limited to 1 site, OR	allowed.	the onset of the rash and on Day 1.	
	elevations in AST/ALT >2x ULN,		Further visit(s) : Appropriate management and follow-up required until resolution of rash or until clinical stability is reached.	

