	OR oral body		Days 2, 3, and 4 : Only if the participant's AST/ALT on Day 0 and/or Day 1 of rash >2x ULN and/or in case of rash progression:	
	temperature		 Additional safety blood samples are required. 	
	≥39.3°C to <40.0°C (≥102.7°F to		• Digital pictures ^d are to be taken.	
	<104.0°F),		Day 5 : Regardless of the Day 0/1 AST/ALT levels or rash progression:	
	OR		 Additional safety blood samples are required. 	
	eosinophils >1,000/mm ³ ,		• Digital pictures ^d are to be taken.	
	OR		After Day 5: Weekly follow-up visits are required (or more frequently at the	
	serum sickness-like		investigator's discretion) as long as Grade 3-4 rash is present. Once Grade 3-4	
	reaction.		rash has resolved to ≤Grade 2 rash, follow-up should be done according to the	
			instructions for follow-up visits for Grade 1 or Grade 2 rash, respectively.	
			 Only if the participant's AST/ALT on Day 5 of rash is still >2x ULN 	
			and/or in case of rash progression, additional safety blood samples and	
			digital pictures ^d are required at these weekly follow-up visits, until resolution or stabilization of the AST/ALT elevations.	
			Upon resolution/stabilization of the rash: Digital pictures ^d should be taken and the final rash assessment pages of the CRF should be completed.	

Status: Approved, Date: 19 July 2023

	Definition	Study Intervention Action	Activities by Day ^a	Referral to Dermatologist and Dermatology Activities
Grade 4 rash ^b	Potentially life-threatening rash with: Extensive or generalized bullous lesions, OR ulceration of mucous membrane involving 2 or more distinct mucosal sites, OR Stevens-Johnson syndrome, OR		 Day 0: Required on-site unscheduled visit for initial rash evaluation, if participant is outside the study site. Day 0 and 1: Safety laboratory assessments are required. Digital pictures^d of skin lesions should be taken within 24 hours after the onset of the rash and on Day 1. Further visit(s): Appropriate management and follow-up required until resolution of rash or until clinical stability is reached. Days 2, 3, and 4: Only if the participant's AST/ALT on Day 0 and/or Day 1 of rash >2x ULN and/or in case of rash progression: Additional safety blood samples are required. Digital pictures^d are to be taken. 	

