- b. The participant should be advised to contact the investigator immediately if there is any worsening of the rash, if any systemic signs or symptoms appear, or if mucosal involvement develops. In case the rash evolves to a higher grade than that first observed, management of the rash should follow the guidelines indicated for the higher grade.
- c. If applicable, dermatologist visit should occur preferably within 24 hours after onset of rash.
- d. Digital pictures to be taken at the study site.

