10.9. Appendix 9: Toxicity Grading Scale for Determining the Severity of Adverse Events

ABBREVIATIONS (used in the table)

ULN=Upper Limit of Normal

IV=Intravenous

LLN=Lower Limit of Normal

Per protocol amendment 3, the toxicity grading scale is replaced with the Division of Acquired Immunodeficiency Syndrome (DAIDS) Table for Grading the Severity of Adult and Pediatric Adverse Events, Version 2.0 (DAIDS 2017) and supplemented with WHO toxicity grading scales where values were absent.

Estimating Severity Grade for Parameters Not Identified in the Grading Table

The functional table below should be used to grade the severity of an AE that is not specifically identified in the grading table. In addition, all deaths related to an AE are to be classified as grade 5.

PARAMETER		GRADE 2 MODERATE		GRADE 4 POTENTIALLY LIFE-THREATENING
event NOT identified elsewhere in the grading table	causing no or minimal interference with usual social & functional activities with intervention not	causing greater than minimal interference with usual social &	inability to perform usual social & functional activities with intervention or hospitalization indicated	Potentially life-threatening symptoms causing inability to perform basic self-care functions with intervention indicated to prevent permanent impairment, persistent disability, or death

Vital Signs ^a	Mild (Grade 1)	Moderate (Grade 2)	Severe (Grade 3)	Potentially Life Threatening (Grade 4)
Fever ^b (°C) (°F)	37.5-to <38.6 or 99.5 to <101.5	≥38.6 to <39.3 or ≥101.5 to <102.7	≥39.3 to <40.0 or ≥102.7 to <104.0	≥40.0 or ≥104.0
Hypertension (with the lowest reading taken after repeat testing during a visit)	140 to < 160 mmHg systolic OR 90 to < 100 mmHg diastolic	≥ 160 to < 180 mmHg systolic OR ≥ 100 to < 110 mmHg diastolic	OR ≥ 110 mmHg diastolic	Life-threatening consequences in a participant not previously diagnosed with hypertension (eg, malignant hypertension) OR Hospitalization indicated

a Participant should be at rest for all vital sign measurements.

b Oral temperature: after no recent hot or cold beverages or smoking.

Systemic (General)	Mild (Grade 1)	Moderate (Grade 2)	Severe (Grade 3)	Potentially Life Threatening (Grade 4)

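### The mandatory stop for febrile rash in Table 5 applies from 39.3°C up to just under 40.0°C and then lapses, so a higher fever gets a weaker rule

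*Protocol*

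**What the plan says.** Section 10.2 sets the scope: "In all cases of rash that are not related to DENV infection, the below rash management should be followed". Follow-up visits and laboratory tests are required where a causal link to study intervention cannot be excluded. The section also concedes that drug rash and dengue rash may be impossible to tell apart.

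Table 5 then assigns actions by grade:

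- **Grades 1 and 2.** "Study intervention intake may be continued at the" investigator's discretion. Dermatology referral is not required.
- **Grade 3.** Permanent discontinuation, withdrawal from the study, no rechallenge, dermatology referral and a biopsy within 24 hours. The qualifying features are diffuse rash with vesicles, a few bullae or mucosal ulceration at one site; AST/ALT above 2x ULN; eosinophils above 1,000/mm³; a serum sickness-like reaction; or an oral temperature of "≥39.3°C to <40.0°C (≥102.7°F to" <104.0°F).
- **Grade 4.** Stevens-Johnson syndrome and toxic epidermal necrolysis qualify, as does a rash that fits this description: "Potentially life-threatening rash with: Extensive or generalized bullous lesions, OR ulceration of mucous membrane involving 2 or more distinct mucosal sites". Temperature does not appear.

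The fever scale in Appendix 9 (Section 10.9) has the same Grade 3 band, with a Grade 4 category above it: "≥40.0 or ≥104.0".

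**The concern.** A stopping rule should not relax as the sign it monitors gets worse. Here the sponsor chose to remove investigator discretion at 39.3°C, but the text gives it back at 40.0°C. The other numeric Grade 3 triggers, for liver enzymes and eosinophils, have no upper limit; only temperature is capped. The band matches the Grade 3 fever band in Appendix 9, which suggests it was carried over without the Grade 4 category that makes a cap workable there.

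What is at stake is participant safety. Rash is a listed risk of the drug: Section 2.3.1 reports two Grade 2 rashes in the first-in-human study that were judged very likely related.

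**Working it through.** There is no plan figure to reproduce. The check applies the Table 5 rows to one rash while only the temperature changes.

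**Assumptions.** The rash falls under Section 10.2 and is diffuse. It has no vesicles, bullae or mucosal ulceration. AST/ALT are at or below 2x ULN and eosinophils at or below 1,000/mm³. There is no serum sickness-like reaction, Stevens-Johnson syndrome or toxic epidermal necrolysis. No other temperature reading is recorded.

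| Oral temperature | Appendix 9 fever grade | Table 5 row met | Action on dosing |
|---|---|---|---|
| 38.0°C | 1 (37.5 to <38.6) | Grade 1 or 2 | Discretion |
| 39.0°C | 2 (38.6 to <39.3) | Grade 1 or 2 | Discretion |
| 39.3°C | 3 (39.3 to <40.0) | Grade 3 | Mandatory stop |
| 39.9°C | 3 (39.3 to <40.0) | Grade 3 | Mandatory stop |
| 40.0°C | 4 (≥40.0) | Grade 1 or 2 | Discretion |
| 40.2°C | 4 (≥40.0) | Grade 1 or 2 | Discretion |

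Width of the band that triggers the stop: 40.0 − 39.3 = 0.7°C. Fever grades that trigger it: 1 of 4.

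**Units.** 39.3 × 1.8 + 32 = 102.74°F and 40.0 × 1.8 + 32 = 104.0°F. The Fahrenheit limits carry the same cap, so this is not a slip in one unit only.

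**Reading of the Grade 3 definition.** The row opens with diffuse rash joined by AND to the skin lesions, followed by a list of ORs. Whether AND binds only to the lesions or to every item, a diffuse rash gives the table above. For a localized rash the reading matters. If AND binds only to the lesions, the table is unchanged. If it governs every item, no temperature triggers the stop.

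**Could another provision restore the automatic stop?**

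- Section 7.1 requires stopping if the investigator believes "it is in the best interest of the participant to discontinue study intervention". That is judgement, with no temperature trigger.
- Section 7.1.1 needs dengue warning signs and hospitalization.
- Section 6.8 covers paracetamol taken for fever of 39°C or more. Temperature is recorded before the dose and one hour after, and "In addition, the Medical Monitor should be informed about this occurrence". It sets no action on study intervention.
- Table 5 note b says that, once a rash worsens in grade, "management of the rash should follow the guidelines indicated for the higher grade". A reading of 40.0°C or above does not by itself meet a higher grade.
- The graded pausing criterion in Section 7.1.3 and the 24-hour notice in Section 8.3.1 concern unsolicited events. Table 3 lists both fever and rash as solicited.

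None of these makes the stop mandatory at 40.0°C or above.

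**The case against.** The strongest case against is that this is an editorial slip with little practical reach. The intent is plain, and most investigators would stop dosing in a participant with rash and a temperature of 40°C. Three conditions must coincide: a temperature of 40.0°C or above, no recorded reading from 39.3 to <40.0°C, and no other Grade 3 or 4 feature. Repeat readings are likely, because temperature is taken daily, whenever the participant feels feverish, and around any paracetamol taken for high fever. One reading inside the band makes the rash Grade 3. Grade 1 and 2 rashes are still seen on site on Day 0 with safety bloods, repeated on Days 1 and 7, so the liver and eosinophil triggers are checked. The serum sickness-like item is also open to clinical judgement at any temperature. And the study has ended.

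Most of this stands, and it limits the size of the point. These cases would be assessed, and many would be stopped by another route. It does not answer the defect itself: the sponsor made the stop mandatory in the lower band, and every remaining route at the higher temperature depends on judgement or on a second finding.

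**Conclusion.** The concern holds. As written, a managed rash whose only severe feature is a temperature of 40.0°C or above loses the mandatory stop, the referral and the biopsy that the same rash would have had at 39.9°C. The automatic stop is under-triggered at the highest fevers.

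The correction is minor but should be made. The documents give no rate of rash with a temperature of 40.0°C or above and report no fever with either first-in-human rash, so no count is estimated.

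The contrast between the two temperatures rests on the rash being diffuse, or on AND binding only to the lesions. The effect on tabulated rash grades is left open: SAP Section 5.6.2 uses Appendix 9, whose rash row has no temperature item, while Protocol Table 3 note c sends rash grading to Section 10.2. Under either, fever of 40.0°C or above is graded 4 in its own right.

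**What to change.** Make the Grade 3 criterion an oral temperature of ≥39.3°C (≥102.7°F) with no upper limit. Alternatively, add ≥40.0°C (≥104.0°F) to the Grade 4 row and state the same mandatory stop there.

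The cost is one cell of Table 5. Section 10.2 refers to dedicated rash pages in the case report form; these are not among the documents, and if they carry the band they need the same edit. No new procedure is introduced, but each participant newly caught would leave the study and have a biopsy within 24 hours, as Grade 3 already requires. SAP Section 1 records that the study ended on 02 October 2024, so the benefit lies in correcting the protocol text and any later protocol that reuses this table.

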10.3. Appendix 3: WHO Clinical Classification of Dengue Disease

ALT = alanine aminotransferase; AST = aspartate aminotransferase; CNS = central nervous system;

DSS = dengue shock syndrome

Source: Muller 2017

a. Fever is defined as an oral body temperature ≥38.0°C (104°F) confirmed by a repeat measurement at least 10 minutes after the first assessment.

Status: Approved, Date: 19 July 2023

10.4. Appendix 4: COVID-19 Appendix

Guidance on Study Conduct During the COVID-19 Pandemic

It is recognized that the COVID-19 pandemic may have an impact on the conduct of this clinical study due to, for example, self-isolation/quarantine by participants and study site personnel; travel restrictions/limited access to public places, including hospitals; study site personnel being reassigned to critical tasks.

In alignment with recent health authority guidance, the sponsor is providing options for study-related participant management in the event of disruption to the conduct of the study. This guidance does not supersede any local or government requirements or the clinical judgment of the investigator to protect the health and well-being of participants and site staff. If, at any time, a participant's safety is considered to be at risk, study intervention will be discontinued, and study follow-up will be conducted.

Scheduled visits that cannot be conducted in person at the study site will be performed to the extent possible remotely/virtually or delayed until such time that on-site visits can be resumed. At each contact, participants will be interviewed to collect safety data. Key efficacy endpoint assessments should be performed if required and as feasible. Participants will also be questioned regarding general health status to fulfill any physical examination requirement.

Every effort should be made to adhere to protocol-specified assessments for participants on study intervention, including follow-up. Modifications to protocol-required assessments may be permitted via COVID-19 Appendix after consultation with the participant, investigator, and the sponsor. Missed assessments/visits will be captured in the clinical trial management system for protocol deviations. Discontinuations of study interventions and withdrawal from the study should be documented with the prefix "COVID-19-related" in the CRF.

The sponsor will continue to monitor the conduct and progress of the clinical study, and any changes will be communicated to the sites and to the health authorities according to local guidance. If a participant has tested positive for COVID-19, the investigator should contact the sponsor's responsible medical officer to discuss plans for study intervention and follow-up. Modifications made to the study conduct as a result of the COVID-19 pandemic should be summarized in the Clinical Study Report.

Guidance Specific to This Protocol

The following emergency provisions are meant to ensure participant and staff safety while site capabilities are compromised by COVID-19-related restrictions. Remote medical consultation and alternatives to clinical laboratory assessments and study intervention administration may allow continued study participation for participants in this study.

As local restrictions are lifted and the acute phase of the COVID-19 pandemic resolves, sites should revert to the original protocol conduct as soon as feasible and in accordance with any country-specific regulatory requirements.

Study Visits and Procedures

- In case **visits** to the study site are not possible, mitigations include; remote (eg, by phone/telemedicine) visits and referral of participants to health care services for safety evaluation, if deemed necessary.
- In case **assessments** cannot be performed per protocol at the study site, alternatives may be possible after discussion and agreement with the sponsor.
 - If certain assessments cannot be performed or are to be performed differently, this is to be documented in the source documents and the (electronic) CRF.
 - There are some assessments that could be conducted remotely via telephone (or videoconference). This methodology can only be used in accordance with applicable (including local) laws, regulations, guidance, and procedures. These remote assessments include review of AEs, concomitant therapy, and questions regarding general health status to fulfill any physical examination requirement.
 - All visits/assessments need to be performed by trained and delegated site staff.
 - Other procedures, eg, imaging, may be conducted at an appropriate facility.

Administration of Study Intervention

Procurement of study intervention by participants (or designee) or shipment of study intervention from the study site directly to participants for at-home administration (including the potential for self-administration of study intervention) could be a possible mitigation.

Exposure to Coronavirus/Development of COVID-19

As for any other comorbidity, the investigator needs to diagnose and treat any (suspected) COVID-19 disease per standard-of-care and per local/national guidance.

If a participant, in any phase of this study, becomes symptomatic for COVID-19 disease, the sponsor suggests that the coronavirus infection should be confirmed by using locally approved laboratory test kits, eg, a diagnostic kit using RT-qPCR. This should be reported to the local health authorities as required.

In addition, the investigator needs to evaluate and discuss with the sponsor's Medical Monitor whether enrollment of a participant with acute COVID-19 infection is in line with the eligibility criteria and whether enrollment of a participant in the study is compromising the participant's safety or the data collection, quality, and interpretation. Special precaution should be taken for those who may carry a higher risk for severe COVID-19 illness.

Impact on Study Data

The sponsor will evaluate the totality of impact of COVID-19 on collection of key study data and additional data analyses will be outlined in study SAP(s).

Monitoring/Audits/Consent/Ethics

Monitoring

Depending on local restrictions, routine on-site monitoring visits may be postponed. The site monitor may set up remote visits in accordance with site and local requirements instead. Additional monitoring visits may be needed in the future to catch up on monitoring activities that can only be performed on-site.

Audits

To comply with national, local, and/or organizational social distancing restrictions due to COVID-19, study site Good Clinical Practices (GCP) audits with direct impact/engagement from the clinical investigator team may not be conducted at the impacted sites. Additional quality assurance activities such as remote audits or focused review of study-related documents may take place with limited impact/engagement if possible.

Consent

Consenting and re-consenting of participants for the measures taken (including also remote consenting by phone or video consultation) will be performed as applicable and according to local guidance for informed consent applicable during the COVID-19 pandemic. The process is to be documented in the source documents.

Ethics

In case of any protocol deviations related to COVID-19, the investigator should notify these to the local IEC/IRB/health authorities per local requirements.

Study Conduct Related to COVID-19 Vaccine Deployment for NonCOVID-19 Clinical Trials

- Participants will be allowed to receive an authorized/licensed COVID-19 vaccine throughout this study, including attenuated COVID-19 vaccines and boosters. The COVID-19 vaccine will be reported as a concomitant medication.
- Side effects of vaccination will be reported as AEs, defining the causality of AEs will rely on the medical judgment of the principal investigator of the study.
- SUSAR reporting must be initiated if the serious adverse reaction is unexpected.
- If the event is serious and considered related to both the COVID-19 vaccine and the study intervention, it has to be recorded as a serious adverse reaction.

